7. SELECTION AND ENROLLMENT OF PARTICIPANTS

The trial will enroll resident and staff in 16 LTCH units with outbreaks of COVID-19 in Ontario. LTCH units will be allocated to receive favipiravir or placebo.

7.1 Eligibility Criteria

7.1.1 Inclusion criteria for LTCHs

- 1. LTCH in Ontario with >80% of residents being adults ≥65 years of age.
- 2. Residents are or can be routinely assessed at least daily by staff.
- 3. LTCH has not previously had a unit enrolled in this study
- 4. Outbreak of COVID-19 declared on at least one nursing unit, requiring all of the following:
 - a. ≥2 to ≤4 residents who develop PCR-confirmed symptomatic COVID-19 infection on the same unit within ≤ 7 days at the time when the outbreak is identified as eligible.
 - b. ≤21 days from symptom onset in the index case at the time when the outbreak is identified as eligible.
 - c. Cumulative attack rate in residents on the affected unit since the beginning of the pandemic ≤25% at the time when the outbreak is identified as eligible.
 - d. ≤20% of residents with microbiologically confirmed COVID-19 or line-listed as a presumptive case in a COVID-19 outbreak and not tested for COVID-19 in prior outbreaks within the last six months.
 - e. Nursing unit with ≥ 16 and ≤ 32 residents.
 - f. Nursing home agrees to work with study coordination to minimize the number of persons who provide care on the unit
- 5. Mechanism exists for delivery of medication and recording of administered medication for all residents.
- 6. ≥80% of residents on outbreak unit are eligible and they or their substitute decision makers consent to participate in the study.
- 7. Written informed consent of Medical Director, Administrator and a delegate of the Residents' Council of the LTCH for LTCH to be included in the cluster trial.

7.1.2 Inclusion criteria for LTCH residents

1. Informed consent from resident or substitute decision maker (SDM),

7.1.3 Inclusion criteria for LTCH staff

- 1. Expected to work at least two 8-hour shifts, or the equivalent time (16 hours on the unit) during the outbreak period.
- 2. Informed consent.

7.2 Exclusion criteria

7.2.1 Exclusion criteria for LTCHs

- 1. Inability to deliver medication to consenting residents within 96 hours of identification of the outbreak.
- 2. Inability to define a physically separate unit with \leq 32 residents.
- 3. Any of facility management, medical advisory committee or resident council do not approve participation.

7.2.2 Exclusion criteria for LTCH Residents and Staff

- 1. Pregnancy (females < 55 years of age require a negative urine pregnancy test at enrollment, and either menopause or two concurrent reliable methods of contraception need to be confirmed)
- 2. History of abnormalities of uric acid metabolism, other than gout.
- 3. History of hypersensitivity to remdesivir or favipiravir
- 4. Previous diagnosis of hepatic cirrhosis
- 5. Current use of the following medications, which cannot be discontinued for the duration of the study: pyrazinamide, hydralazine, more than 3000 mg of acetaminophen per day

7.3 Consent and Enrollment

The Medical Director, the LTCH Administrator and a delegate of the Residents' Council of the LTCH will give written informed consent for the LTCH to be included in the cluster trial. The LTCH Administrator will then delegate the personal distribution of a fact sheet describing the trial to all potentially eligible LTCH staff, residents and SDMs. The fact sheet will indicate that LTCH staff, residents and their SDMs would be contacted by research personnel in case of a COVID-19 outbreak in the LTCH, and offer them the possibility to opt out from being contacted by research personnel by calling or emailing the administration of the LTCH. In addition, posters about the trial will be placed in all staff locker rooms, lounges and nursing stations, and in public areas of the home.

LTCH staff, residents and their SDMs who did not opt out within 5 calendar days after receipt of the fact sheet will be contacted by research personnel. The study will be explained to each person, and written informed consent or e-consent will be obtained. This consent will include all features required for obtaining full informed consent, as outlined in the 2nd edition of the Tri-Council Policy Statement on Ethical Conduct of Research Involving Humans (TCPS2). LTCH staff and competent residents who provide written informed consent or e-consent at this stage may be enrolled into the trial. Residents who have been assessed as not competent to make their own medical decisions in their capacity evaluation

(https://collections.ola.org/mon/24004/300799.pdf) may be enrolled into the trial if their SDM provided written informed consent or e-consent.

For this trial, time to randomization and treatment is of considerable importance for outbreak control; thus, if written informed consent or e-consent has not been obtained prior to an outbreak being declared, informed consent will occur in two stages to minimize delays. LTCH staff, residents and/or their SDMs who have not opted out, but have not yet given written informed consent or e-consent, will therefore be asked to give preliminary consent by telephone or video call ≥24 hours after receipt of the fact sheet describing the trial. This consent will also include all features required for obtaining full informed consent, as outlined in the 2nd edition of

the Tri-Council Policy Statement on Ethical Conduct of Research Involving Humans (TCPS2), ⁶⁶ and will be fully documented by the research personnel. Those who provide preliminary verbal consent at this stage may be enrolled into the trial. LTCH staff and competent residents who provide preliminary consent at this stage may be enrolled into the trial. Residents who are not considered competent to provide consent (see above) may be enrolled into the trial if their SDM provided preliminary consent. A second stage of the consent process in participants with preliminary consent will involve obtaining a signed copy of the REB-approved written informed consent form, either in electronic or hard copy, or e-consent. This stage should be done as soon as possible after the verbal preliminary consent is obtained, and research personnel will obtain a signed copy of the consent form or e-consent no later than 40 days after randomization

As new staff may be needed on the unit over time, any new staff starting work on the outbreak LTCH unit will be identified by the facility and referred to the trial for consenting and enrolment on an ongoing basis using the process described above.

7.5 Co-enrollment Guidelines

Co-enrollment into other Health Canada-regulated clinical trials of COVID-19 prevention is permitted, but details of the co-intervention must be documented in the study database. For participants who develop microbiologically confirmed COVID-19 infection, enrollment in trials of treatment other than favipiravir is permitted, but details of the co-intervention must be documented in the study database.

8. WITHDRAWAL OF PARTICIPANTS

8.1 Withdrawal criteria, and criteria for discontinuation of study drug

Participants may be withdrawn from the study if the Sponsor terminates the trial. Participants who are discovered to be pregnant will have the study drug discontinued due to potential teratogenicity; however, given the age distribution of LTCH residents (<3% under 65 years of age), pregnancy in this patient population is extremely unlikely. If a new health condition emerges in a participant that requires medication contraindicated by the protocol, then decisions regarding dose modification or discontinuation of the study drug can be made at the discretion of the study investigators and/or the attending physician, but the participant will be retained in the study for ascertainment of the primary and secondary outcomes.

Participants or their most responsible physician may discontinue study drug at any time if severe adverse events thought to be due to study drug are identified. Participants will continue in the study if this occurs, and the reason discontinuation of study drug will be noted in the study database. Participants may withdraw from the study at any point for any reason.

9. ALLOCATION AND BLINDING PROCEDURES

9.1 Allocation

Each nursing home unit will only be randomized once all members of the unit or their substitute decision makers (SDMs) give preliminary consent, decline or are classified as not contactable; at least 80% of residents or their SDMs within the unit must give consent to take the study medication (favipiravir or placebo) for unit eligibility for randomization. Every effort will be made to contact residents and/or their substitute decision makers within 48 hours. Those who cannot be contacted within 96 hours will not be eligible to receive study drug. LTCH staff may be enrolled on a continuing basis, recognizing that new LTCH staff may be needed to start work on the unit during the outbreak.

As LTCH units will be enrolled prospectively, we will use probabilistic minimization on the baseline COVID-19 attack rate on the unit to allocate units 1:1 (8 intervention units, 8 control units) to the 2 groups. Probabilistic minimization will be performed by an independent statistician at the Applied Health Research Centre (AHRC) at St. Michael's Hospital using the R package *minirand* (R Foundation for Statistical Computing, Vienna, Austria). Consent of LTCH staff and residents prior to randomization of the cluster, and use of placebo as a control intervention will help minimize the risk of "empty" clusters or the use of interventions that are not part of this protocol.

Each person for whom written informed or preliminary verbal consent was obtained will be entered in the electronic case report form (eCRF) so that an adequate number of uniquely coded study drug bottles/blister packes for all consenting members of the LTCH unit can be prepared. An automated audit trail will record the time, date, allocation, and participant identification numbers. Those who withdraw preliminary consent or decline study drug will be asked to consent to be followed-up for primary and secondary outcome. Those who also decline follow-up will be excluded from intention-to-treat analyses. Waiver of consent will be requested of participating sites to record the number of non-participating residents and LTCH staff, and the number and date of onset of cases of symptomatic microbiologically confirmed COVID-19 in these two groups.

9.2 Blinding

The trial will be blinded with the use of placebo controls. Favipiravir will have a placebo which is similar in size and shape, but can be distinguished because of color differences and an imprint on the surface of favipiravir tablets which could not be matched for the placebo given the timelines of this trial. However, favipiravir and placebo will be packaged in blister packages of identical appearance.

Drug supply will be dispensed by external pharmacies, which supply multiple LTCHs, therefore we will not be able to completely rule out that pharmacists dispensing medication will remain blinded. In addition, both placebo and favipiravir can be crushed before administration, which is necessary for some residents, and will not be identical in appearance when crushed. However, since favipiravir is not otherwise available in Canada, residents of included LTCHs will only receive one type of intervention (either drug or placebo, depending on the allocation of the LTCH unit), and no information will be provided by external pharmacies, research personnel or investigators to the LTCHs about, color, imprinting, appearance after crushing, and about the allocated intervention. Therefore, it is unlikely that LTCH staff and residents will be unblinded.

All study investigators will be blinded, except for an independent statistician from AHRC who will be responsible for probabilistic minimization, but will otherwise not be involved in the conduct of the trial. Outcome assessors, who will extract outcome data from the LTCHs' administrative data, will be blind to treatment allocation. The statistician conducting the analysis will also be unaware of treatment allocation.

9.3 Emergency unblinding

Code breaks should occur only in exceptional circumstances when knowledge of the actual treatment is absolutely essential for further management of the patient. The resident's attending physician and/or the LTCH Medical Director or Directors of Nursing are encouraged to discuss with the Principal Investigator if they believe that unblinding is necessary. If unblinding is considered necessary, the Principal Investigator will contact the independent statistician at the AHRC, who will do the code break as deemed necessary and communicate it directly to resident's attending physician. Similarly, a staff member's family or attending physician will be encouraged to consult with the Principal Investigator the need to unblind for LTCH staff.

Medical directors, investigators and research personnel are encouraged to maintain the blind as far as possible. The actual allocation must not be disclosed to LTCH staff or patients and/or other research personnel, investigators or sponsors. In addition, there should not be any disclosure of the code in any of the corresponding patient documents. Medical director and Principal Investigator must report all code breaks with reason as they occur on the corresponding CRF page. Unblinding should not necessarily be a reason for study drug discontinuation.

10. STUDY INTERVENTIONS

10.1 Favipiravir

The study intervention is a 25-day course of favipiravir/placebo for LTCH residents and staff, to be initiated immediately after recognition of the LTCH outbreak.

Favipiravir was approved for novel influenza strains unresponsive to standard antiviral therapies in Japan in 2004, under the trade name Avigan®. It is manufactured by Fujifilm Toyama Chemical Co., Ltd. Favipiravir is a purine nucleoside analogue, which acts as a competitive inhibitor of RNA-dependant RNA polymerase. It has in-vitro activity against influenza A and B including activity against amantadine-, oseltamivir-, and zanamivir-resistant influenza viruses, and several agents of viral hemorrhagic fever, and SARS-CoV-2 *in vitro*. A1-43,71

The duration of prophylaxis was defined to align with the sum of the periods of infectivity and incubation. The average incubation period ranges between 4-6.4 days (ranging from 0-14 days), ^{5,23,75,76} with a 95th percentile of 12.5 days. Further, preliminary literature from Germany suggests that the duration of infectivity is 7-10 days from the onset of symptoms. Prophylaxis will continue until day 25.

New staff starting to work on the unit after day 1 who consent to receiving study drug will continue the drug until day 25 of the outbreak.

Residents in the LTCH unit diagnosed with COVID-19 at enrollment will be offered treatment with study drug for 14 days.

10.1.1 Dosing and Administration

The dosage for favipiravir to be used in this study for prophylaxis is 1600 mg (8 x 200 mg tablets) orally twice daily on day 1 followed by 800 mg (4 x 200 mg tablets) orally twice daily. The dose for treatment is 2000 mg orally twice daily on day 1, the 1000 mg orally twice daily for 13 additional days.

Favipiravir is provided as 200 mg tablets and dosed orally. Favipiravir is rapidly and completely absorbed after oral administration of the 200 mg immediate release tablets. If necessary, favipiravir may be crushed for administration and can be taken with or without food.

This dosing strategy is increased from the licensed dosing regimen for influenza, to account for the higher in-vitro concentrations required for activity against SARS-CoV-2. Elevated dosing strategies, up to 6000 mg on day 1 followed by 1200 mg BID has been used in published Favipiravir studies for Ebola. Prolonged administration to 22 days has been explored in a phase 1 study in Japan (JP120) with a favorable safety profile (patients received 1800 mg PO BID on day 1 followed by 800 mg PO BID from day 2-21 and a single dose of 800 mg on day 22).

10.1.2 Dosing in special populations

Favipiravir is contraindicated in nursing mothers and pregnant women or women of child-bearing age who are not taking oral contraception due to its potential teratogenicity.

No alteration of dosing is needed in subjects with renal impairment. Total exposure for plasma favipiravir for subjects with severe renal impairment (Stage 4) was 1.3-fold higher compared to subjects with normal renal function. No obvious effect of renal impairment on safety was observed and favipiravir treatment was generally well tolerated in subjects with renal impairment.

No alterations in dosing strategies are required in older adults. The maximum plasma concentration and AUC values in elderly subjects in a single and a multiple-dose study completed in Japan were higher than in young subjects. Comparing AUC values on Day 5, the differences were 40 and 80% after 600 mg once a day and 400 mg BID, respectively. In the companion study completed in the United States of America, there were no differences between young and older populations based on Day 5 AUC comparison in subjects receiving either 600 or 800 mg BID.

Higher drug levels occur in patients with hepatic impairment, and we have excluded patients with cirrhosis.

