4.3 Potential Risks and Benefits to Human Participants

Overall, more than 40 clinical studies with favipiravir have been conducted globally, mainly in the US and Japan. Favipiravir has been well tolerated in studies in adults and elderly subjects with uncomplicated influenza. A consistent safety profile composed of relatively low frequencies of mild to moderate adverse events clustering around the system organ classes of gastrointestinal disorders has been characterized. Mild to moderate transient, asymptomatic elevations in serum uric acid and mild to moderate diarrhea are the two most common adverse events known to occur with favipiravir. Favipiravir has been safely studied with therapy durations up to 22 days (JP120, Phase 1 study).

Favipiravir is considered a safe drug. No related serious adverse events occurred in licensure studies of favipiravir. ⁷¹ Preclinical and animal studies show no direct suppression of white blood cell types or immunosuppression by favipiravir. Genotoxicity studies indicate that favipiravir does not pose a clinical genotoxic risk; however, based on the results of embryo-fetal toxicity studies, favipiravir is not recommended for use in pregnant females, those who may become pregnant, or those who are nursing. Though an inhibitor of CYP 2C8 and aldehyde oxidase, few drugs are contra-indicated. Overall, the safety of favipiravir suggests that the potential benefit to human participants exposed to a confirmed case of COVID-19 generally outweighs potential risks.

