6. STUDY OBJECTIVES AND DESIGN

6.1 Overall Study Design (figure 1)

This study is a partially blinded, placebo-controlled cluster randomized trial of chemoprophylaxis to control outbreaks of COVID-19 in LCTHs for the elderly. The unit of analysis is a ward/unit. This design is selected to mimic the current approach to outbreaks of other respiratory viral infections, both because this approach has proven effective for these other viruses, and because it is standard practice and therefore feasible to implement.

Eligible LTCHs will be asked to report outbreaks to the study in addition to the legally-required reporting to their local public health unit; public health units will also be asked to discuss the study with LTCHs reporting outbreaks. In addition, study staff will contact the infection control practitioner in each of the screened LTCHs twice weekly, to ensure the prompt identification of outbreak units.

Either pre-study, or at baseline (identification of the outbreak), residents and staff will be assessed for contraindications to enrollment and informed consent will be obtained for residents and staff to receive the allocated intervention, and to be followed up individually for clinical outcomes, adherence and safety during the outbreak. Favipiravir or placebo will be offered to all residents and staff who will be working on the unit during the chemoprophylaxis period, according to the allocation. Surveillance for infection will occur as usual for resident illness within each facility; staff will be asked to report symptoms and will be screened for symptoms each time they enter the building. Consenting residents and staff will be screened at day 0, day 14 and day 40 to identify asymptomatic infections and to assess duration of viral shedding. The primary outcome will be control of the outbreak, defined as no new microbiologically confirmed case of COVID-19 for 24 consecutive days up to day 40.

STUDY SCHEME

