10.1.7 Additional Safety Considerations

For the purpose of this trial, the following are exclusion criteria for study drug administration:

- 1. Pregnancy
- 2. History of abnormalities of uric acid metabolism, other than gout.
- 3. Subject has a history of hypersensitivity to remdesivir or favipiravir
- 4. Known hepatic cirrhosis
- 5. Current use of the following medications, which cannot be discontinued for the duration of the study: pyrazinamide, hydralazine, more than 3000 mg of acetaminophen per day.

The following safety considerations are based on data from individuals taking favipiravir for influenza. They are listed here for reference.

- *Phototoxicity*: Nonclinical studies have shown mild phototoxicity. One study subject experienced mild photosensitivity (rash) following a tanning bed session. All subjects should avoid excessive exposure to sunlight or artificial ultraviolet light.
- *Laboratory Values*: Mild to moderate asymptomatic elevations of uric acid and aminotransferase have been observed in healthy volunteers and subjects with influenza treated with favipiravir in clinical studies. The changes have been reversible upon favipiravir discontinuation.
- *Mutagenesis:* Favipiravir proved mildly positive under some conditions studied in the mammalian chromosomal aberration test and mouse lymphoma assays at high concentrations. Although the potential for genotoxicity at high exposures cannot be ruled

- out, evidence indicates that this risk is minimal at the exposures planned in this clinical study.
- GI Tract Lesions: In two proof-of-concept studies of orally administered favipiravir against Ebola virus infection in macaques, GI tract lesions were observed that were not consistent with the known natural history of Ebola nor with previous animal and clinical studies of favipiravir. However, evidence suggests that bacterial infections and preexisting enterocolitis in the treated macaques may have been responsible, and an ongoing risk to patients may not exist.

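### The protocol calls favipiravir contraindicated in nursing mothers, but neither exclusion list names breastfeeding, so a breastfeeding staff member could be missed at screening

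*Protocol*

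**What the plan says.** Protocol section 10.1.2, on dosing in special populations, states: "Favipiravir is contraindicated in nursing mothers and pregnant women or women of child-bearing age who are not taking oral contraception". The same section covers liver disease: "Higher drug levels occur in patients with hepatic impairment, and we have excluded patients with cirrhosis". Section 4.3 is softer on reproduction and lactation, saying the drug is "not recommended for use in pregnant females, those who may become pregnant, or those who are nursing".

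Eligibility is set elsewhere. Section 7.2.2 lists five exclusion criteria for residents and staff. In short form they are pregnancy, disordered uric acid metabolism other than gout, hypersensitivity to remdesivir or favipiravir, cirrhosis, and certain medications that cannot be stopped. The pregnancy item requires a negative urine test in females under 55 and adds that "either menopause or two concurrent reliable methods of contraception need to be confirmed". The cirrhosis item reads "Previous diagnosis of hepatic cirrhosis". Section 10.1.7 repeats the five topics with the introduction that "the following are exclusion criteria for study drug administration"; there the pregnancy item is the single word, without the test or contraception rule.

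Staff inclusion (7.1.3) asks for consent and one other condition: "Expected to work at least two 8-hour shifts, or the equivalent time (16 hours on the unit) during the outbreak period". Section 6.1 offers study drug to staff working on the unit as well as to residents, and says that "residents and staff will be assessed for contraindications to enrollment and informed consent will be obtained".

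**The concern.** A contraindication that the protocol itself states does not appear in the lists that screeners apply. Someone working through 7.2.2 or 10.1.7 would find nothing to stop a breastfeeding staff member from entering the trial and receiving up to 25 days of drug, at a dose that 10.1.1 describes as raised above the licensed influenza regimen.

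The group can be reached. Residents are almost all beyond child-bearing age, but staff are not, and 7.2.2 itself provides for females under 55. New staff join throughout the outbreak by the same consent and enrolment process (7.3) and take drug until day 25 (10.1). Consent can be verbal at first and is sought within 48 to 96 hours of an outbreak, which is when screeners rely most on a list.

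What is at stake is participant safety, possibly including that of a nursing infant. No estimate or test in the trial depends on it.

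**Working it through.** No formula applies. The check sets the groups that 10.1.2 says should not receive the drug against the two operative lists.

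| Group in 10.1.2 | In 7.2.2? | In 10.1.7? |
|---|---|---|
| Pregnant | Yes, item 1 | Yes, item 1 |
| Child-bearing age without contraception | Yes, within item 1, in different terms | No |
| Cirrhosis | Yes, item 4 | Yes, item 4 |
| Nursing | No | No |

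1. *Count.* Section 7.2.2 carries 3 of the 4 groups and 10.1.7 carries 2 of the 4. Nursing is the only group in neither. Counted by criterion, it appears in 0 of 5 items in 7.2.2 and 0 of 5 in 10.1.7. The second list repeats the topics of the first, so this is one omission made twice rather than ten independent misses.

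2. *Other places where it could appear.* As a lactation status, nursing occurs only in 4.3 and 10.1.2. It is absent from the staff inclusion criteria (7.1.3), the screening steps (13.2), the staff schedule of events (Table 2), the reasons for stopping drug (8.1, which names pregnancy) and the pregnancy section (11.1).

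3. *Whether another criterion catches it by proxy.* A urine pregnancy test does not detect lactation, and neither does confirming two contraceptive methods. None of the uric acid, hypersensitivity, cirrhosis or medication items bears on it. A breastfeeding staff member who expects to work the required hours, consents, tests negative and uses two reliable methods therefore passes every listed criterion, provided none of those other items applies.

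4. *Whether the omission looks deliberate.* No section gives a reason for it. Section 10.1.2 links its liver warning to an exclusion that does exist; its nursing warning has no counterpart.

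5. *Number affected.* The protocol gives neither a staff count nor the share who are breastfeeding, so no number is calculated.

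**The case against.** The strongest reply is that 10.1.2 is itself a binding part of the protocol. It sits under Study Interventions and states a contraindication outright. Section 6.1 requires an assessment for contraindications, a physician confirms eligibility (13.3, Medical Oversight), section 16 obliges investigators to know the protocol and product monograph, and 17.1.2 forbids deviations without sponsor approval except to remove an immediate hazard. Nothing in the protocol permits dosing a nursing mother. On this view the point is a missing cross-reference. It stands in part: the rule exists, and the fault is that the lists do not reflect it. But each safeguard is general, and none puts nursing in front of the person screening.

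Three further points are fair and limit the claim:

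- Section 13.2 and the staff schedule itemise no exclusion criterion at all, not even the pregnancy test. Their silence on nursing adds little; the case rests on the two lists.
- The questionnaires are in an appendix that is not available, the consent pages were removed, and the Operations Manual is not available. Any of these might mention breastfeeding. A question on a form could catch the case in practice, but the criteria would still be wrong.
- The contraception rules differ: 10.1.2 refers to oral contraception, while 7.2.2 accepts any two reliable methods. So the contraception group is carried over only in altered form. That is a second, smaller mismatch, and it does not explain the absence of nursing.

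It can also be said that the only reason 10.1.2 gives is potential teratogenicity, that no lactation hazard is described, and that with 1:1 allocation about half the units receive placebo. This bears on how large any harm might be. It does not justify lists that admit a group the protocol calls contraindicated.

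**Conclusion.** The point holds. The contraindication for nursing mothers in 10.1.2 is absent from both exclusion lists, and a breastfeeding staff member can satisfy every listed criterion. The omission itself is certain from the text. That such a person could be missed at screening is a reasonable inference, which assumes that the unseen forms do not ask.

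It should be fixed, but its reach is narrow. In practice it concerns staff only. The size of any harm cannot be judged, because the protocol gives no lactation data and no basis for a head count. The primary endpoint, the sample size and the analysis do not depend on it.

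**What to change.** By amendment:

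- Add current breastfeeding as a sixth criterion in 7.2.2 and in 10.1.7.
- Ask about it at the day 0 staff eligibility assessment (13.2 and the staff schedule of events), and put the same question to staff who join after day 1 under 7.3. If the existing questionnaire already asks, confirming that is enough for this item.
- Optionally, name breastfeeding in 8.1 as a reason to stop study drug, and bring the contraception wording in 10.1.2 and 10.1.7 into line with 7.2.2.

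The cost is one line in each list and one screening question. Any breastfeeding staff would go without study drug, as 10.1.2 already intends. The 80% threshold for randomizing a unit counts residents (7.1.1 and 9.1), so excluding a staff member does not affect unit eligibility. Allocation, sample size and analysis stay as they are.
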